3.2 Primary Endpoints – Pharmacokinetic Parameters

The following PK parameters will be derived as primary endpoints:

• AUC _{0-inf}	Area under the concentration-time curve from time zero (predose) extrapolated to infinity calculated by linear up/log down trapezoidal summation and extrapolated to infinity by the addition of the last quantifiable concentration divided by the terminal rate constant
• AUC _{0-last}	Area under the concentration-time curve from time zero (predose) to the last measurable concentration calculated by linear up/log down trapezoidal summation
• C _{max}	Maximum observed serum concentration
• t _{max}	Time to achieve maximum observed serum concentration
• t _{1/2}	Terminal phase elimination half-life, calculated as $\ln(2)/\lambda_Z$ where λ_Z is the first-order rate constant associated with the terminal (log-linear) elimination phase
• CL/F	Apparent clearance, estimated as dose divided by AUC _{0-inf}
• V _{ss} /F	Apparent steady-state volume of distribution, estimated as CL/F*MRT, where MRT=(AUMC _{0-inf})/(AUC _{0-inf}).

In addition, the following PK parameter will be derived:

- V_Z/F: Apparent volume of distribution (based on terminal phase), estimated as CL/F*1/ λ_Z .

3.3 Secondary Endpoint – Immunogenicity

The presence or absence of ADA to tezepelumab will be determined from the blood samples collected for immunogenicity testing. A tiered testing scheme will be employed, with the first step being screening. Samples found putative positive in the screening step will be tested in the confirmatory step. Samples confirmed positive for ADA in the confirmatory step will undergo titre determination. Samples confirmed positive for ADA will be archived for possible testing for neutralising antibodies (nAb). A patient is defined as being ADA-positive if a positive ADA result is available at any time, including baseline and all post-baseline measurements; otherwise ADA negative.

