9.4.2.2 Secondary Endpoints

The prevalence and incidence of ADA to tezepelumab will be reported using the safety analysis set. Anti-drug antibodies data will be summarised using descriptive statistics by visit. Samples confirmed positive for ADA will be archived for possible testing for nAb. The potential effects of ADA on PK and safety will be evaluated, if appropriate.

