2.1.2 Safety Analysis Set

The safety analysis set will consist of all subjects who receive at least one dose of tezepelumab.

Anti-drug antibodies, PD parameter summaries and safety presentations will be based on the safety analysis set.

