4 ANALYSIS METHODS

4.1 General Principles

The analyses will be performed by IQVIA using the SAS® (Statistical Analysis Software; SAS Institute, Inc., Cary, North Carolina) statistical software system version 9.4 or higher. All analyses will be performed according to AZ standard operating procedures unless otherwise stated herein.

After the last subject has completed their Visit 9, the database for the study will be locked and the data will be reported in a CSR.

All individual data as recorded in the final study database, after the last subject has completed their Visit 9, will be provided by IQVIA Data Management.

No formal statistical hypothesis tests will be made. Data will be provided in data listings sorted by subject number. Tabular summaries will be presented.

For qualitative variables and categorical data, the population size (N), number of patients with available data (n), and the percentage (of available data) for each class of the variable will be presented. Percentages will be rounded to 1 decimal place.

Quantitative data, including PK data, will be summarised using descriptive statistics, including N, n, mean, standard deviation (SD), 1st quartile (Q1), median, 3rd quartile (Q3), minimum (min), and maximum (max), unless stated otherwise.

Additionally, coefficient of variation (CV%), geometric mean, geometric SD, and geometric coefficient of variation (GCV%) will be reported for PK concentrations and parameters, except t_{max} which will be summarized using n, median, min and max. These results will be presented in tables and figures as applicable.

Geometric mean is calculated as $\exp[\mu]$, where μ is the mean of log-transformed data.

GCV% is calculated as $100 \sqrt{[\exp(s^2) - 1]}$, where s is the SD of log-transformed data.

For non-PK data the mean, median, and first and third quartiles (where applicable) will be presented with one more decimal place than the raw data, the SD will be presented with two more decimal places than the raw data, and min and max values will have the same number of decimal places as the raw data.

For all serum concentrations and PK parameters for tezepelumab, data and descriptive statistics will be presented in summary tables and by-subject listings as described in [Table 3](#), but the calculation of summary statistics will be performed using unrounded data.

Table 3 **Conventions for Reporting of Pharmacokinetic Data**

Variable/ Parameter	Data in Listings	Reporting in Summary Tables			

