4.2.5 Immunogenicity

All listings and summaries of ADA results will be based on the safety analysis set.

Immunogenicity of tezepelumab (ADA) results will be listed by subjects with any positive ADA result at any time first, followed by subjects with no positive ADA result by scheduled visit. The corresponding titre summaries (e.g. 1st quartile, median, 3rd quartile) of each ADA category will be provided, and will be based on the maximum titre of all positive samples for each subject.

The ADA status across the study for each subject will also be classified and listed as per the following categories:

- Subjects who are ADA positive at any time including baseline and/or post-baseline (ADA prevalence).
- Subjects who are ADA positive at baseline only.
- Subjects who are ADA positive at baseline and positive in at least one post baseline measurement.
- Subjects who are ADA positive at baseline regardless of post-baseline result.
- Subjects who are ADA positive post-baseline.
- Subjects who are ADA positive post-baseline and ADA negative at baseline (treatment induced ADA positive)
- Subjects who are treatment boosted ADA positive, defined as baseline positive ADA titre that was boosted to a 4 fold or higher level following IP administration
- Subjects who are treatment emergent ADA (TE-ADA) positive (ADA incidence): defined as either treatment induced ADA positive or treatment boosted ADA positive.

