4.2.5.1 Potential effects of ADA on PK

The impact of ADA on PK will be explored using the PK analysis set.

The impact of ADA on PK will be explored by comparing individual serum tezepelumab concentration time profiles in ADA positive (any time) and ADA negative subjects.

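### The SAP labels every child without a positive ADA result as ADA negative, has no not-evaluable class, and does not say whether untested children count in the ADA percentages

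*SAP*

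**What the plan says.** ADA presence is the only secondary endpoint (SAP 1.1.2). SAP 3.3 defines it at subject level as a two-way split. A child is positive if a positive result "is available at any time, including baseline and all post-baseline measurements; otherwise ADA negative".

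The population is the safety set. SAP 4.2.5 states: "All listings and summaries of ADA results will be based on the safety analysis set". Protocol 9.4.2.2 agrees: "The prevalence and incidence of ADA to tezepelumab will be reported using the safety analysis set". Entry to that set depends on dosing alone: "The safety analysis set will consist of all subjects who receive at least one dose of tezepelumab" (SAP 2.1.2).

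Protocol 8.5.2.1 schedules one pre-dose ADA sample on Day 1 and two post-dose samples, on Day 29 and Day 85/EOS. Unscheduled samples are taken only for a suspected immunological event. Under Protocol 7.2, a child who withdraws has an EOS visit only if that is possible.

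Two other parts of the SAP bear on the point. Section 4.1 says that categorical summaries give the "number of patients with available data (n), and the percentage (of available data) for each class of the variable will be presented". Section 4.2.5 defines prevalence (positive at any time) separately from incidence (treatment-induced or treatment-boosted). It lists baseline-only positives as their own category, but names no denominator for any category.

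SAP 4.2.5.1 then compares individual concentration-time profiles in "ADA positive (any time) and ADA negative subjects".

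**The concern.** The final clause of SAP 3.3 covers two different children: one who was tested and found negative, and one who was not tested. For incidence, the second kind includes any child without a post-dose sample, because treatment-emergent ADA cannot be observed without one.

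The case is foreseeable. The plan doses about 14 children so that at least 12 complete. Non-completers may be replaced (Protocol 7.2.1), but a dosed child who is replaced stays in the safety set.

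Two outputs are exposed. The first is the reported ADA incidence, where an untested child may sit in the denominator as if known to be negative. The second is the ADA-PK comparison. The PK set needs only one usable detectable post-dose concentration (SAP 2.1.3), so a child who leaves early, with a short profile and no post-dose ADA test, can be shown as an ADA-negative profile. With so few children, the reader needs to know how many were actually tested.

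**Working it through.** Neither document gives an expected ADA rate for this trial or a calculated sample size, so there is no figure of the plan's own to reproduce.

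**Which rule governs an untested child?**

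- SAP 3.3 gives every subject a status. On that reading all safety-set children have available data, and the percentage base is the whole set.
- SAP 4.1 bases the percentage on children with data. If an untested child has no ADA data, that child drops out of the base.
- SAP 4.2.5 does not choose between these. Its incidence categories say who is positive and define no treatment-emergent-negative group.
- SAP 4.2.5.1 involves no percentage, so 4.1 does not help there. The label from 3.3 stands.

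**Inputs.** Dosed children: 14 (SAP 1.3, approximate). Planned completers: at least 12 (same place). Children with no post-dose ADA result: *m*. The documents do not give *m*, so I show 0 to 4; *m* = 2 assumes that both planned non-completers leave without a post-dose sample. Children with treatment-emergent ADA: *x*.

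**Formulas.** Untested children counted as negative: *x*/14. Evaluable children only: *x*/(14 − *m*). The ratio of the first to the second is (14 − *m*)/14.

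| *m* | Ratio | *x* = 1: *x*/14 against *x*/(14 − *m*) | Shortfall, points | *x* = 2: *x*/14 against *x*/(14 − *m*) | Shortfall, points |
|---|---|---|---|---|---|
| 0 | 1.00 | 7.1% against 7.1% | 0 | 14.3% against 14.3% | 0 |
| 1 | 0.93 | 7.1% against 7.7% | 0.5 | 14.3% against 15.4% | 1.1 |
| 2 | 0.86 | 7.1% against 8.3% | 1.2 | 14.3% against 16.7% | 2.4 |
| 3 | 0.79 | 7.1% against 9.1% | 1.9 | 14.3% against 18.2% | 3.9 |
| 4 | 0.71 | 7.1% against 10.0% | 2.9 | 14.3% against 20.0% | 5.7 |

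With *x* = 0 the percentage is 0% either way.

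**Precision, for scale only.** The exact (Clopper-Pearson) 95% interval for 1/14 is 0.2% to 33.9%, and for 1/12 it is 0.2% to 38.5%. With no positives, the upper limit is 23.2% for 0/14 and 26.5% for 0/12.

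**How likely is a positive child?** Protocol 2.2 gives 4.9% treatment-emergent ADA in the Phase 3 study of adults and adolescents. If that rate applied here (an assumption), the chance of at least one positive among 12 tested children would be 1 − 0.951^12 = 45%. The expected reported rate with *m* = 2 would be 4.9% × 12/14 = 4.2%.

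**The opposite direction.** Treatment-induced ADA requires a negative baseline. Suppose one child has no baseline result and a positive post-baseline result, and the other 13 are fully tested and negative. If the missing baseline is read as negative, incidence is 1/14 = 7.1%. If that child is not evaluable, it is 0/13 = 0%. SAP 3.1.1 leaves a missing baseline as missing, which argues against the first reading, but SAP 4.2.5 does not say how such a child is classed.

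**The case against.** The strongest case on the other side is that this needs at most a clarification. SAP 4.1 already bases percentages on available data, and the safety set may fix only the N shown beside them. Section 3.3 defines positivity at any time, which is prevalence; incidence has its own definitions in 4.2.5, and none of them places an untested child in a negative class. For prevalence, a child with a negative Day 1 sample and nothing later has been tested and is properly negative. Gaps would also be partly visible, because ADA is summarised by visit and listed by subject. The loss may be smaller than two children: a non-completer who leaves after Day 29 would normally have a post-dose sample, and SAP 3.1.4 allows early-discontinuation measurements to be used.

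Most of this stands, and it limits the point. It does not remove it. Section 4.1 settles the matter only if an untested child has no ADA data, and 3.3 gives that child a status. It does not reach the profile comparison at all.

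A reader might infer more than the documents support:

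- *That incidence is necessarily understated.* It is not. That needs an untested child, a denominator that keeps the child and, for the percentage to move, at least one positive child. A missing baseline could work the other way.
- *That the rule makes a planned upper bound look too tight.* Neither document plans a confidence interval for ADA.
- *That the adolescent study in Protocol 2.2 shows a baseline-only positive.* That subject had ADA both before and after dosing.
- *That 4.2.5.1 must be regrouped by treatment-emergent ADA.* Grouping by any-time ADA is a legitimate choice when the question is whether ADA affects PK, and 4.2.5 already lists baseline-only positives separately.

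**Conclusion.** The point holds in a limited form. SAP 3.3 states a catch-all that labels untested children negative, SAP 4.1 points the other way for percentages, and the SAP does not say which governs.

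The effect on incidence is conditional and small: 1.2 percentage points for one positive child if 2 of 14 lack a post-dose result, and 0 to 2.9 points as that number runs from 0 to 4. These shifts are well inside the exact intervals, and no hypothesis test depends on them. The direction is downward for missing post-dose results and could be upward for a missing baseline. In the ADA-PK comparison the consequence is a wrong label on an individual profile, which does not depend on any denominator.

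The change is still worth making. It corrects a stated rule for the only secondary endpoint and tells the reader how many children the result rests on. The figures assume 14 dosed children; the number without a post-dose result is not in the documents.

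**What to change.** 1. In SAP 3.3, replace the final clause with: *ADA negative if at least one valid result is available and none is positive; otherwise not evaluable.*
2. In SAP 4.2.5, state the denominators: for prevalence, children with at least one valid ADA result; for incidence (TE-ADA), children with a valid baseline result and at least one valid post-baseline result.
3. Report the number of children not evaluable for each.
4. In SAP 4.2.5.1, do not plot children without a post-baseline ADA result as ADA negative. Show them as not evaluable or leave them out, and say which.

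Flagging baseline-only positives in the 4.2.5.1 plots, using the categories already in 4.2.5, is optional.

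The cost is a few sentences in the SAP and a change of denominator in the ADA tables. No extra sample or visit is needed. Denominators become slightly smaller and, where post-dose results are missing, percentages slightly less favourable.

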3.4 Safety Endpoints

Safety and tolerability will be assessed in terms of AEs (including SAEs), laboratory data, vital signs, and ECGs.

3.4.1 Adverse Events

Adverse events (including SAEs) experienced by any subject at any time during the entire study will be coded using the latest version of the Medical Dictionary for Regulatory Activities (MedDRA) at the time of database lock.

Adverse events will be categorised for analysis according to their onset date into the following study periods described in Section 3.1.3:

- AEs occurring during the screening period: date of informed consent \leq AE onset date $<$ date of dose of IP,
- AEs occurring during the on-study period: date of dose of IP \leq AE onset date \leq date of study completion or date of withdrawal from study.

If the AE has a completely missing (and unresolvable) onset date, then the AE will be considered an on-study event, unless the end date indicates unambiguously that the AE resolved before treatment started. If the AE has a partially missing (and unresolvable) onset date, then the AE will also be considered an on-study event, unless either the end date indicates unambiguously that the AE resolved before treatment started, or the imputed partial onset date is prior to start of treatment.

The handling of partial/missing dates for AEs is detailed in [Appendix A](#).

Adverse Events of Special Interest

Certain preferred terms, groups of preferred terms, or standardised MedDRA queries (SMQs) are being identified as being of special scientific and medical interest towards improving the understanding of tezepelumab. The list of terms used to identify adverse events of special interest (AESIs) may be updated on an ongoing basis as new safety data are accumulated.

The protocol specifies Adverse Events of Special Interest (AESIs) as those which merit special attention in this trial, and for which derivation details (for those derived from the eCRF), or a statement when the derivation needs to be referenced externally to the SAP (for those derived from MedDRA dictionary terms), are given in [Appendix B](#).

3.4.2 Clinical Laboratory

Samples for determination of clinical chemistry, haematology, virology and urinalysis will be taken at the times detailed in Table 1 of the CSP and assessed in a central laboratory. The

parameters outlined in Table 9 of the CSP will be measured and reported in standard international (SI) units.

There will be no imputation for missing values. For values recorded with a leading greater than or less than ('>', '<') symbol, the reported numeric value will be used for analysis and the value with the symbol will be included in the listings, unless otherwise specified. For example, a value of <0.01 will be analysed as 0.01 and listed as <0.01.

Urinalysis data will be categorised as negative (0) or positive (+) at each visit.

The investigator will assess the available lab results with regards to clinically relevant abnormalities. Absolute values will be compared to the relevant reference range and classified as low (below range), normal (within range or on limits) or high (above range). The central laboratory reference ranges that will be used will follow the most recent version of the AZ standard reference ranges and unit conversion external data. All absolute values falling outside the AZ provided reference ranges will be flagged in the listings. These classifications will also be used for shift tables.

For the purpose of shift tables, baseline will be defined as specified in [Section 3.1.1](#). Maximum or minimum value post-baseline will be calculated over the entire post-baseline period.

For the liver function tests: aspartate aminotransferase (AST), alanine aminotransferase (ALT), alkaline phosphatase (ALP) and total bilirubin (TBL), the multiple of the central laboratory upper limit of the normal (ULN) range will be calculated for each data point:

Multiple = Value / ULN,

i.e. if the ALT value was 72 and the ULN 36, then the multiple would be 2.

3.4.3 Vital Signs

Vital signs (systolic blood pressure, diastolic blood pressure, pulse rate, weight, height, Body mass index (BMI), respiratory rate and body temperature) will be assessed.

Vital sign results will be compared to the given reference ranges ([Table 2](#)) and classified as low (below range), normal (within range or on limits) or high (above range). All results falling outside the reference ranges will be flagged in the listings. The investigator will assess the results with regards to clinically relevant abnormalities. In addition, changes in vital signs between baseline and each subsequent scheduled assessment will be calculated.

Table 2 Vital Signs Reference Ranges for Age 5-11 Years

[figure not shown]
Parameter	Standard Units	Lower Limit	Upper Limit
Diastolic Blood Pressure	mmHg	57	80
Systolic Blood Pressure	mmHg	97	120
Pulse Rate	bpm	70	110
Respiratory Rate	breaths/min	20	30
Body Temperature	°C	35.5	37.5
Weight	kg	15	NA

3.4.4 **Electrocardiograms**

[figure not shown]
A 12-lead ECG will be performed at timelines as specified in Table 1 of the CSP, using local site equipment after at least 5 minutes of rest for the subject in a quiet setting without distractions.

The outcome of the investigator's overall ECG evaluation will be recorded as normal/abnormal in the CRF and with any abnormalities recorded as not clinically significant or clinically significant.

CCI

CCI

4 ANALYSIS METHODS

4.1 General Principles

The analyses will be performed by IQVIA using the SAS® (Statistical Analysis Software; SAS Institute, Inc., Cary, North Carolina) statistical software system version 9.4 or higher. All analyses will be performed according to AZ standard operating procedures unless otherwise stated herein.

After the last subject has completed their Visit 9, the database for the study will be locked and the data will be reported in a CSR.

All individual data as recorded in the final study database, after the last subject has completed their Visit 9, will be provided by IQVIA Data Management.

No formal statistical hypothesis tests will be made. Data will be provided in data listings sorted by subject number. Tabular summaries will be presented.

For qualitative variables and categorical data, the population size (N), number of patients with available data (n), and the percentage (of available data) for each class of the variable will be presented. Percentages will be rounded to 1 decimal place.

Quantitative data, including PK data, will be summarised using descriptive statistics, including N, n, mean, standard deviation (SD), 1st quartile (Q1), median, 3rd quartile (Q3), minimum (min), and maximum (max), unless stated otherwise.

Additionally, coefficient of variation (CV%), geometric mean, geometric SD, and geometric coefficient of variation (GCV%) will be reported for PK concentrations and parameters, except t_{max} which will be summarized using n, median, min and max. These results will be presented in tables and figures as applicable.

Geometric mean is calculated as $\exp[\mu]$, where μ is the mean of log-transformed data.

GCV% is calculated as $100 \sqrt{[\exp(s^2) - 1]}$, where s is the SD of log-transformed data.

For non-PK data the mean, median, and first and third quartiles (where applicable) will be presented with one more decimal place than the raw data, the SD will be presented with two more decimal places than the raw data, and min and max values will have the same number of decimal places as the raw data.

For all serum concentrations and PK parameters for tezepelumab, data and descriptive statistics will be presented in summary tables and by-subject listings as described in [Table 3](#), but the calculation of summary statistics will be performed using unrounded data.

Table 3 **Conventions for Reporting of Pharmacokinetic Data**

Variable/ Parameter	Data in Listings	Reporting in Summary Tables			
		Geometric Mean	Mean, SD, Median	Min, Max	CV%, GCV%
Serum concentrations	AR, up to 4 dp	AR+1, up to 4dp	AR+1, up to 4dp	AR, up to 4 dp (a)	1dp
AUC _{0-inf}	3sf	3sf	3sf	3sf	3sf
AUC _{0-last}	3sf	3sf	3sf	3sf	3sf
C _{max}	3sf	3sf	3sf	3sf	3sf
t _{max}	2dp	NA	Median 2dp	2dp	NA
t _{1/2}	3sf	3sf	3sf	3sf	3sf
CL/F	3sf	3sf	3sf	3sf	3sf
V _{ss} /F	3sf	3sf	3sf	3sf	3sf
V _r /F	3sf	3sf	3sf	3sf	3sf
λ _Z	4sf	4sf	4sf	4sf	4sf

NA Not applicable; sf Significant figures; dp Decimal places; AR As Reported

(a) AR except in the scenario where ½ LLOQ is the min; refer to Section 4.2.4.2.

(b) Serum concentrations will be converted to $\mu\text{g}/\text{mL}$ for the listings and summary statistics.

(c) Time variables will be converted to days.

The treatment will be labelled in the relevant PK, PD, and safety summaries and data listings as “Tezepelumab CCI SC”.

